7.4.1 Main Analysis

The primary efficacy endpoint will be analyzed using an analysis of covariance (ANCOVA) model based on the ITT population. The ANCOVA model will include both the treatment groups and the presence/absence of endothelial hypercellularity at baseline as factors and adjust for the sPCR at baseline (as a covariate). If required and when possible, missing Week 24 data will be imputed using an appropriate Multiple Imputation (MI) procedure. Should Multiple Imputation procedures fail, last observation carried forward (LOCF) will be used as an alternative imputation algorithm.

The regression method for monotone missing data (SAS PROC MI) will be used for multiple imputation. For patients who discontinued the study due to adverse events, consider the missing data mechanism for the missing change from baseline values to be missing not at random (MNAR). For patients who discontinued the study due to reasons other than adverse events or patients who completed the study but have missing data at a visit, consider the missing data mechanism for the missing change from baseline values to be missing at random (MAR).

Missing data will be imputed in two separate subgroups. The first subgroup will contain all patients randomized to a Fostamatinib group that have data available at the visit or have a MAR missing data mechanism. The second subgroup will contain all patients randomized to placebo as well as fostamatinib patients missing data at the visit with an MNAR missing data mechanism.

Multiple imputation will then be performed within each subgroup, resulting in missing data for Fostamatinib patients under an MAR missing data mechanism imputed from a model obtained only from Fostamatinib treated patients, and missing data from all placebo patients as well as Fostamatinib treated patients with an MNAR missing data mechanism imputed from a model obtained only from placebo treated patients. After obtaining complete data sets for both subgroups, the complete data sets after combining subgroups will be used in the analysis, and inferences from each complete dataset will be combined to obtain an overall test statistic.

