7.4.2 Sensitivity Analyses

While the inferential analysis methodology will remain unchanged for sensitivity analyses of the primary endpoint, one method of imputing missing data will be performed before inferential analysis:

The LOCF procedure in the ITT population – This analysis will use an ANCOVA model. The ANCOVA model will include both the treatment group and the presence/absence of endothelial hypercellularity at baseline as factors and adjust for the sPCR at baseline (as a covariate). Dependent variable is change from baseline to Week 24 in sPCR. Missing Week 24 data will be imputed using the LOCF procedure. Pre-treatment values will not be carried forward.

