Systolic and Diastolic Blood Pressure Abnormalities

Classification	Upper Limit of Blood Pressure (mm Hg)	
	Systolic	Diastolic
Normal	less than 120	and Less than 80
Elevated	120 – 129	and Less than 80
Stage 1	130 – 139	or 80 – 89
Stage 2	140 or Higher	or 90 or Higher
Hypertensive Crisis	Higher than 180	or Higher than 120

If a subject’s blood pressure satisfies more than one classification, the more severe classification will be assigned. Classifications above are ordered in from less severe to most severe.

For the purpose of analysis of shift in vital signs will be considered normal according to the following cut offs:

Vital Sign Normal Ranges

Vital Sign	Normal Range
Systolic/Diastolic blood pressure	Less than 120/80 mm Hg
Heart rate	50 – 100 beats/min

D. Assessment of Renal Biopsies

The following data will be obtained for each biopsy:

- Total number of glomeruli (a minimum of 8)
- Number of glomeruli with global sclerosis
- Number of glomeruli with segmental sclerosis

For each glomerulus in the biopsy the following will be assessed (see Table 6):

- Mesangial hypercellularity
- Endocapillary hypercellularity (absent, segmental or global)
- Presence of crescents (cellular/fibrocellular or fibrous)

From the above assessments a MEST score will be calculated.

Table 6: Oxford Classification of Renal Biopsy Scoring

Variable	Definition	Score
Mesangial hypercellularity	<4 Mesangial cells/mesangial area=0	M0
	4–5 Mesangial cells/mesangial area=1	M1
	6–7 Mesangial cells/mesangial area=2	
	≥ 8 Mesangial cells/mesangial area=3	
	The mesangial hypercellularity score is the mean score for all glomeruli	
Segmental glomerulosclerosis	Any amount of the tuft involved in sclerosis, but not involving the whole tuft or the presence of an adhesion	S0-absent S1-present
Endocapillary hypercellularity	Hypercellularity due to increased number of cells within glomerular capillary lumina causing narrowing of the lumina	E0-absent E1-present
Tubular atrophy/interstitial fibrosis	Percentage of cortical area involved by the tubular atrophy or interstitial fibrosis, whichever is greater	T0-0-25% T1-26-50% T2->50%

E. Example SAS Code of Multiple Imputation

Step 1: Impute non-monotone missing visits using MCMC

```
proc mi data=TEMP seed=007 nimpute=10 out=OUTMI_1;
  mcmc impute=monotone chain=multiple;
  var trt1 trt2 endohbl base visit3--visit9;
run;
```

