Step 2a: Impute monotone missing visit using a monotone regression model for non-placebo subjects who discontinued for reasons other than AE

```
proc mi data=OUTMI_1 seed=007 nimpute=1 out=OUTMI_2A;
  where trt01pn>1 & comp24wk^='ADVERSE EVENT';
  class trt01pn endohbl;
  monotone reg(visit9);
  var trt01pn endohbl base visit3--visit9;
run;
```

Step 2b: Impute monotone missing visit using a monotone regression model for placebo subjects or non-placebo subjects who discontinued due AE

```
proc mi data=OUTMI_1 seed=007 nimpute=1 out=OUTMI_2B;
  where trt01pn=1 or (trt01pn>1 & comp24wk='ADVERSE EVENT');
  class endohbl;
  monotone reg(visit9);
  var endohbl base visit3--visit9;
run;
```

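### The SAP's example imputation code omits BY _Imputation_ in Steps 2a and 2b, so pooling its output would lose most of the between-imputation variance of the primary analysis

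*SAP*

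**What the plan says.** SAP 7.4.1 makes multiple imputation the main handling of missing Week 24 sPCR. Fostamatinib subjects whose data are treated as missing at random are imputed from a fostamatinib model. Placebo subjects, and fostamatinib subjects who stop for AEs, are imputed from a placebo model. After that, "inferences from each complete dataset will be combined to obtain an overall test statistic".

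Appendix E, headed "Example SAS Code of Multiple Imputation", gives the code:

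- Step 1 is "proc mi data=TEMP seed=007 nimpute=10 out=OUTMI_1" with the option "mcmc impute=monotone chain=multiple". It fills only intermittent gaps, writes ten stacked copies and leaves post-dropout values missing.
- Step 2a (fostamatinib, non-AE) is "proc mi data=OUTMI_1 seed=007 nimpute=1 out=OUTMI_2A".
- Step 2b (placebo, plus fostamatinib AE dropouts) is "proc mi data=OUTMI_1 seed=007 nimpute=1 out=OUTMI_2B", with the model list "var endohbl base visit3--visit9".

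Neither Step 2 call has a BY statement, and the imputation index is in neither VAR list. The appendix stops before recombination, ANCOVA and pooling. The sensitivity analysis in 7.4.2 is separate: "Missing Week 24 data will be imputed using the LOCF procedure".

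**The concern.** Rubin's rules measure the uncertainty due to missing data by how much the estimate varies between completed datasets. That works only if each dataset has its own draw of the imputation model's parameters. As printed, ten near-identical copies of the same subjects enter one regression, one set of coefficients is drawn, and all ten datasets share it. Only row-level residual noise still differs between copies, and its variance is also too small.

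A programmer who follows the appendix and then pools as 7.4.1 requires would understate the standard error of the primary contrast. The two-sided 5% test could then exceed its level.

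**Working it through.** **Inputs.** 25 subjects per arm, 25 placebo against 50 pooled fostamatinib, and CV 0.923 (SAP 3.2). Ten imputations and the VAR lists (Appendix E). Two-sided 5% (SAP section 7). The documents state no dropout rate, AE share of dropout or visit correlation, so these are assumed.

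**Plan's own figure.** Log SD = √ln(1 + 0.923²) = 0.785, and a 43% reduction is ln 0.57 = −0.562. A t-test with 25 against 50 has 82.2% power, consistent with the stated 80%. The SAP gives no figure for between-imputation variance.

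**Closed form.** Let n be the subjects with observed Visit 9 data and k the number of regression parameters. Stacking ten copies multiplies both the residual sum of squares and X′X by 10, and changes the residual df from n − k to 10n − k. Hence:

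- residual variance ratio = 10(n − k)/(10n − k) = (n − k)/(n − k/10);
- coefficient variance ratio = one tenth of that.

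Step 2b at Visit 9 has an intercept, endohbl, base and Visits 3–8, so k = 9. Step 2a adds treatment, so k = 10.

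| Step | n | df correct | df as printed | Residual variance ratio | Coefficient variance ratio |
|---|---|---|---|---|---|
| 2b | 20 | 11 | 191 | 11/19.1 = 0.58 | 0.058 |
| 2b | 25 | 16 | 241 | 16/24.1 = 0.66 | 0.066 |
| 2a | 40 | 30 | 390 | 30/39 = 0.77 | 0.077 |
| 2a | 50 | 40 | 490 | 40/49 = 0.82 | 0.082 |

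These ratios are exact if Step 1 has no intermittent gaps to fill, and approximate otherwise.

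**Simulation of the consequence.** No treatment effect, log SD 0.785, monotone dropout with the first missing visit uniform over Visits 5–9, and ten imputations. Three correlation structures were used: random intercept 0.4 plus AR(1) 0.6, exchangeable 0.5 and exchangeable 0.7. The contrast is the ANCOVA comparison of pooled fostamatinib with placebo, pooled by Rubin's rules with Barnard–Rubin df. There were about 2,400 runs per scenario, and the Monte Carlo SE of the type I error is about 0.4–0.6 points. It assumes that the Step 1 index survives Step 2. With all dropout non-AE:

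| Dropout | Between-imputation variance kept | Pooled SE below true SD | Type I error as printed |
|---|---|---|---|
| 5% | 39–40% | 1–3% | 5.2–5.9% |
| 10% | 33–37% | 3–6% | 5.5–6.2% |
| 20% | 23–26% | 7–8% | 6.0–6.9% |
| 30% | 7–16% | 14–15% | 8.5–9.2% |

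With Rubin's original df the maximum is 9.8%. With half of fostamatinib dropouts due to AEs, the SE is within 3% of the true SD and type I error is 4.2–5.6%. LOCF in the same runs gave 4.4–5.6%.

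**Repeat simulations.** A separate run (1,200 per scenario, two correlation structures, non-AE dropout of 10/20/30%) kept 33–35/23–27/6–13% of the variance, with type I error 5.5–5.7/6.9–7.4/9.3–9.6%. A third set (300–600 runs, 4–32% dropout, 0, 50 or 100% of fostamatinib dropouts due to AEs) kept 24–48% on average. Its type I error as printed was 2.3–7.0%, with Monte Carlo error of about 1 point. That confirms the variance loss but does not by itself show clear inflation.

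**The case against.** The strongest reply is that Appendix E does not govern. It is an example, 7.4.1 never cites it, and SAP 11.1 points to the efficacy section for the imputation details. The wording of 7.4.1 is sound, and the code cannot run as the primary analysis because it has no pooling step. All of this is true. But 7.4.1 gives no number of imputations, seed or predictor list, and does not say that Step 2 runs once per imputation. A programmer has only the appendix for those.

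Second, the inflation depends on dropout being unrelated to AEs, although the protocol has several AE-driven reasons to stop treatment. This stands in part. At 20% dropout with a quarter of fostamatinib dropouts due to AEs, type I error as printed was 4.9–5.3% in one simulation and 5.3–5.6% in another. At 30% dropout with a quarter due to AEs it was still 7.3–7.6%. The relief comes from conservatism in the placebo-based imputation offsetting the error, not from valid code.

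Third, the documents do not say whether the imputation index survives Step 2. If it is lost, the type I figures above do not apply and the ten sets cannot be separated for pooling. A careful programmer should notice. Analysing all rows as one dataset gave a simulated type I error of 49–59%.

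Fourth, early withdrawals have a Visit 9-equivalent assessment (Protocol 7.9), and from Day 148 the SAP's visit windows count it as Week 24. No simulation modelled this, so some post-dropout information is ignored. This limitation stands.

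**Conclusion.** The concern holds. The missing BY statement is plain in the code and conflicts with the pooling that 7.4.1 describes. The loss of most of the between-imputation variance is firm: at most 48% was kept, on average, in any simulated scenario.

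The effect on the primary test is conditional. It is small at 5–10% dropout, material from about 20% when dropout is mostly not AE-related, and close to nil when half of fostamatinib dropouts are due to AEs. These sizes rest on the assumed dropout rates, timing and correlations, and on the index being retained. The LOCF sensitivity analysis is unaffected. This should be fixed before the primary analysis is programmed, but it does not undermine the design or the method stated in words.

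**What to change.** Sort OUTMI_1 by `_Imputation_` and add `by _Imputation_;` to Steps 2a and 2b. Keep the index in both outputs, recombine OUTMI_2A and OUTMI_2B, run the ANCOVA by `_Imputation_`, and pool. Show these last steps in Appendix E so that it matches 7.4.1. No endpoint, population or analysis model changes.

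The cost is a few lines of code and a larger standard error. With non-AE dropout the pooled SE rises by about 4% at 5% dropout, 8–9% at 10%, 19–22% at 20% and 38–43% at 30%. Part of that rise is conservatism: the corrected SE is 1–5% above the true SD at 5–10% dropout and 9–18% above at 20–30%, with type I error 2.3–4.9%. With AE-related dropouts it is more conservative still (SE 6–35% above the true SD, type I error 1.0–3.2%), because of the placebo-based imputation that 7.4.1 prescribes. One contributor to the conservatism is that Step 2b fits 9 parameters on at most 25 placebo subjects. That is separate from the missing BY statement and is no reason to leave it out.
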